3.3 Missing Data and Data Conventions 13

4. CHANGES FROM THE PROTOCOL..... 14

APPENDIX 1 CTCAE V4.03 GRADING FOR LABORATORY VALUES 15

Confidential Document

	CCB-CRISIS-01 Statistical Analysis Plan	Revision No. 1.0
	Document Date: 17-Dec-2020	Page 5 of 17

List of Abbreviations

AE	Adverse Event
ALP	Alkaline Phosphatase
ALT	Alanine Aminotransferase
AST	Aspartate Aminotransferase
CI	Confidence Interval
COVID-19	Coronavirus Disease 2019
CTCAE	Common Terminology Criteria for Adverse Events
DHO	Dihydroorotate
DHODH	Dihydroorotate Dehydrogenase
DSMB	Data Safety Monitoring Board
EHR	Electronic Health Record
ICU	Intensive Care Unit
LLN	Lower Limit of Normal
LLOQ	Lower Limit of Quantification
mITT	Modified Intent-to-Treat
MedDRA	Medical Dictionary for Regulatory Activities
NEWS2	National Early Warning System 2
Q1	First Quartile
Q3	Third Quartile
RNA	Ribonucleic Acid
SARS-CoV-2	Severe Acute Respiratory Syndrome Coronavirus 2
SE	Standard Error
SOC	Standard of Care
TEAE	Treatment-Emergent Adverse Event
ULN	Upper Limit of Normal
WBC	White Blood Cell
WHODrug	World Health Organization Drug Dictionary

Confidential Document

	CCB-CRISIS-01 Statistical Analysis Plan	Revision No. 1.0
	Document Date: 17-Dec-2020	Page 6 of 17

1. INTRODUCTION

1.1 Background

Beginning in December 2019, Chinese scientists isolated a novel coronavirus, severe acute respiratory syndrome coronavirus 2 (SARS-CoV-2) from patients with virus-infected pneumonia which was later designated as coronavirus disease 2019 (COVID-19) by the World Health Organization (WHO). Approximately 14% of those affected with this virus will develop severe disease requiring hospitalization and oxygen support; 5% will require admission to the intensive care unit (ICU). Coronaviruses, like other Ribonucleic acid (RNA) based viruses, do not have the machinery to synthesize their own nucleotides and thus depend upon the host intracellular pool of nucleotides for viral replication. In essence, viruses steal the host RNA building blocks, and without these building blocks they are unable to replicate.

Dihydroorotate dehydrogenase (DHODH) is a clear therapeutic target for the inhibition of host pyrimidine synthesis. Brequinar is an orally available and potent inhibitor of DHODH. Brequinar is one of more than 300 quinoline-carboxylic acid derivatives prepared in an analog synthesis program in the 1980s, which was started after it was found that a compound of this class had antitumor activity.

The CRISIS trial will study standard of care (SOC) and SOC with 5 days of DHODH inhibition. Clear Creek Bio hypothesizes that a defined 5-day course of brequinar will inhibit the enzyme DHODH to a degree sufficient to result in the transient depletion of host pyrimidine nucleotides, thereby inhibiting viral replication.

1.2 Trial Design

This will be a phase 1a randomized, open label, multi-center study with approximately 24 subjects. All subjects will receive SOC per institutional guidelines for treatment of patients with COVID-19 infection. In addition to SOC, the brequinar group will receive brequinar 100 mg once daily for 5 days.

Subjects will have a Screening Visit followed as soon as possible with Study Day 1 (Day 1 may take place on the same day if entry criteria data are available). Subjects will be followed through Day 15, with mortality assessed via a phone call/other digital media acceptable to institution on Day 29.

Confidential Document

	CCB-CRISIS-01 Statistical Analysis Plan	Revision No. 1.0
	Document Date: 17-Dec-2020	Page 7 of 17

1.2.1 Number of Subjects and Randomization

Subjects who meet all the inclusion and none of the exclusion criteria will be enrolled in the study until approximately 24 subjects have completed the study. Subjects will be randomized to either SOC or SOC plus brequinar or in a 1:2: ratio (approximately 8 subjects assigned to SOC alone and approximately 16 subjects on SOC plus brequinar).

1.3 Trial Objectives

1.3.1 Primary Objectives

The primary objective of this study is to determine the safety and tolerability of SOC and SOC plus brequinar in hospitalized COVID-19 subjects.

1.3.2 Secondary Objectives

The secondary objectives of this study are

- To determine the changes in clinical status measures through Day 15
 - hospitalization status
 - duration of hospitalization
 - NEWS2 Score
- To determine survival status through Day 29

1.3.3 Exploratory Objectives

- To determine the change in SARS-CoV-2 nasopharyngeal viral load through Day 15
- To determine the change in inflammatory markers through Day 15
- To determine the change in DHO levels through Day 15
- To determine the change in brequinar concentration levels through Day 7

2. STATISTICAL METHODOLOGY

2.1 General Principles

In general, continuous parameters will be summarized by number of non-missing observations (N), mean, standard error (SE), median, quartiles, minimum, and maximum. Categorical parameters will be summarized by count and percentage of the non-missing observations, and

Confidential Document

	CCB-CRISIS-01 Statistical Analysis Plan	Revision No. 1.0
	Document Date: 17-Dec-2020	Page 8 of 17

95% confidence interval (CI), when appropriate. All statistical analyses will be performed using SAS® Version 9.4. Adverse events (AEs), procedures and medical history will be coded using Medical Dictionary for Regulatory Activities (MedDRA) Version 23.0. Prior and concomitant medications will be coded using World Health Organization Drug Dictionary (WHODrug) Enhanced March 2020. Common Terminology Criteria for Adverse Events (CTCAE) Version 4.03 will be utilized for adverse event and laboratory reporting.

All study data collected will be presented in listings.

2.2 Sample Size Determination

Formal sample size calculations are not applicable for this phase 1a, open label study. Up to 24 subjects are planned to be entered in this trial. Additional subjects may be enrolled following data review.

2.3 Trial Populations

The modified Intent to Treat (mITT) population will include all randomized subjects who had at least one post-randomization assessment, and who received at least one dose of study medication if randomized to SOC + Brequinar group. All analyses will be based on the mITT population.

2.4 Subject Accounting and Baseline Characteristics

Demographics and baseline characteristics (including NEWS2 score and ICU level of care at randomization) will be summarized by treatment. Prior and concomitant medications/procedures will be summarized by treatment. A medication/procedure may be classified as both prior and concomitant. Medical history will be summarized by treatment.

2.5 Efficacy Analyses

2.5.1 Primary Efficacy Analyses

None

2.5.2 Secondary Efficacy Analyses

Hospitalization Status and Duration

Hospitalization status (died, hospitalized in ICU, hospitalized not in ICU, discharged for initial hospitalization and re-hospitalization) will be summarized on Study Day 3, 5, 7 and 15. Kaplan

Confidential Document

	CCB-CRISIS-01 Statistical Analysis Plan	Revision No. 1.0
	Document Date: 17-Dec-2020	Page 9 of 17

Meier estimates and plots will be provided to assess the duration of hospitalization (Study Day at time of initial discharge). Subjects who were not discharged by the Day 15 visit will be censored at the Day 15 visit. Subjects who did not complete the trial while still hospitalized will be censored at the date of last contact.

NEWS2 Score

Changes from baseline to Day 3, 5, 7, and 15 in NEWS2 scores will be summarized by treatment. In addition, the NEWS2 scores will be summarized by category (0-4, 5-6, 7 or above). The NEWS2 parameters will be summarized at each visit, including changes from baseline for continuous parameters. (See [Section 3.2](#) for derivation of NEWS2 score).

Mortality

Mortality will be summarized through Day 29 by treatment group. Kaplan Meier estimates and plots will be provided to assess the time to death (date of death minus date of randomization). Subjects who are alive at the Day 29 contact will be censored at the Day 29 contact. Subjects whose Day 29 survival is unknown will be censored at the date of last contact.

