	SOC + Brequinar (N=xx) n (%)	SOC (N=xx) n (%)
Overall		
Completed the study (through Day 15)	xx (xx.x)	xx (xx.x)
Discontinued	xx (xx.x)	xx (xx.x)
Physician Decision	xx (xx.x)	xx (xx.x)
Adverse Event	xx (xx.x)	xx (xx.x)
Withdrawal by Subject	xx (xx.x)	xx (xx.x)
Study Terminated by Sponsor	xx (xx.x)	xx (xx.x)
Protocol Violation	xx (xx.x)	xx (xx.x)
Lost to Follow-Up	xx (xx.x)	xx (xx.x)
Other	xx (xx.x)	xx (xx.x)
Site xx		
Completed the study (through Day 15)	xx (xx.x)	xx (xx.x)
Discontinued	xx (xx.x)	xx (xx.x)
Physician Decision	xx (xx.x)	xx (xx.x)
Adverse Event	xx (xx.x)	xx (xx.x)
Withdrawal by Subject	xx (xx.x)	xx (xx.x)
Study Terminated by Sponsor	xx (xx.x)	xx (xx.x)
Protocol Violation	xx (xx.x)	xx (xx.x)
Lost to Follow-Up	xx (xx.x)	xx (xx.x)
Other	xx (xx.x)	xx (xx.x)
Source: Listing 16.X.X.X		

Programming note: Sort in descending frequency based on the number of subjects in the SOC + Brequinar group, except for “Other” that shall stay at the last row. Sort alphabetically to break ties.

Clear Creek Bio, Inc.: Protocol CCB-CRISIS-01

Table 14.1.3

Summary of Demographics and Baseline Characteristics by Treatment
Modified Intent-to-Treat Population

Parameter	SOC + Brequinar (N=xx)	SOC (N=xx)
Age (years)		
n	xx	xx
Mean (SE)	xx.x (xx.xx)	xx.x (xx.xx)
Median	xx.x	xx.x
Q1, Q3	xx.x, xx.x	xx.x, xx.x
Min, Max	xx, xx	xx, xx
Sex, [n (%)]		
Male	xx (xx.x)	xx (xx.x)
Female	xx (xx.x)	xx (xx.x)
Ethnicity, [n (%)]		
Hispanic or Latino	xx (xx.x)	xx (xx.x)
Not Hispanic or Latino	xx (xx.x)	xx (xx.x)
Race, [n (%)]		
White	xx (xx.x)	xx (xx.x)
Black or African American	xx (xx.x)	xx (xx.x)
Asian	xx (xx.x)	xx (xx.x)
American Indian or Alaska Native	xx (xx.x)	xx (xx.x)
Native Hawaiian or Other Pacific Islander	xx (xx.x)	xx (xx.x)
Other	xx (xx.x)	xx (xx.x)
Height (cm)		
n	xx	xx
Mean (SE)	xx.x (xx.xx)	xx.x (xx.xx)
Median	xx.x	xx.x
Q1, Q3	xx.x, xx.x	xx.x, xx.x
Min, Max	xx, xx	xx, xx
Weight (kg)		
n	xx	xx
Mean (SE)	xx.x (xx.xx)	xx.x (xx.xx)
Median	xx.x	xx.x
Q1, Q3	xx.x, xx.x	xx.x, xx.x
Min, Max	xx, xx	xx, xx
BSA (m2)		
n	xx	xx
Mean (SE)	xx.x (xx.xx)	xx.x (xx.xx)
Median	xx.x	xx.x
Q1, Q3	xx.x, xx.x	xx.x, xx.x
Min, Max	xx, xx	xx, xx
Source: Listing 16.X.X.X		

Clear Creek Bio, Inc.: Protocol CCB-CRISIS-01

Table 14.1.3

Summary of Demographics and Baseline Characteristics by Treatment

Intent-to-Treat Population

Parameter	SOC + Brequinar (N=xx)	SOC (N=xx)
NEWS2 Score		
n	xx	xx
Mean (SE)	xx.x (xx.xx)	xx.x (xx.xx)
Median	xx.x	xx.x
Q1, Q3	xx.x, xx.x	xx.x, xx.x
Min, Max	xx, xx	xx, xx

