Re-Hospitalization	xx (xx.x)	xx (xx.x)
Missing	xx	xx
etc.		
Study Day 15		
Died	xx (xx.x)	xx (xx.x)
Hospitalized in ICU	xx (xx.x)	xx (xx.x)
Initial Hospitalization	xx (xx.x)	xx (xx.x)
Re-Hospitalization	xx (xx.x)	xx (xx.x)
Hospitalized (not ICU)	xx (xx.x)	xx (xx.x)
Initial Hospitalization	xx (xx.x)	xx (xx.x)
Re-Hospitalization	xx (xx.x)	xx (xx.x)
Discharged	xx (xx.x)	xx (xx.x)
Initial Hospitalization	xx (xx.x)	xx (xx.x)
Re-Hospitalization	xx (xx.x)	xx (xx.x)
Missing	xx	xx
Day 29 Contact		
Died	xx (xx.x)	xx (xx.x)
Alive	xx (xx.x)	xx (xx.x)
Missing	xx	xx
Source: Listing 16.x.x.x		

Programming notes: summarize hospitalization status and death on Study Day 3, 5, 7, 15; summarize only death on Day 29. Include missing rows to capture unknown status.

Clear Creek Bio, Inc.: Protocol CCB-CRISIS-01

Table 14.2.2.1

Summary of Kaplan Meier Estimates for Duration of Hospitalization by Treatment
Modified Intent-to-Treat Population

	SOC + Brequinar (N=xx)	SOC (N=xx)
Total Patients Discharged	xx	xx
Number of Censored ^a	xx	xx
Not Discharged by Day 15 Visit	xx	xx
Did Not Complete Study	xx	xx
Q1	xx	xx
Median	xx	xx
Q3	xx	xx
Note: Duration of hospitalization is defined as Study Day at time of initial discharge. a: Subjects who were not discharged by the Day 15 visit will be censored at the Day 15 visit. Subjects who did not complete the trial while still hospitalized will be censored at the date of last contact. Source: Listing 16.x.x.x		

Clear Creek Bio, Inc.: Protocol CCB-CRISIS-01
Figure 14.2.2.2
Duration of Hospitalization by Treatment
Modified Intent-to-Treat Population

Note: Duration of hospitalization is defined as the Study Day at time of initial discharge. Subjects who were not discharged by the Day 15 visit will be censored at the Day 15 visit. Subjects who did not complete the trial while still hospitalized will be censored at the date of last contact.
Source: 16.x.x.x

Clear Creek Bio, Inc.: Protocol CCB-CRISIS-01

Table 14.2.3.1

Summary of Kaplan Meier Estimates for Time to Death by Treatment
Modified Intent-to-Treat Population

	SOC + Brequinar (N=xx)	SOC (N=xx)
Number of Deaths	xx	xx
Number of Censored ^a	xx	xx
Alive at Day 29 Contact	xx	xx
Unknown	xx	xx
Q1	xx	xx
Median	xx	xx
Q3	xx	xx
a: Subjects who are alive at the Day 29 contact will be censored at the Day 29 contact. Subjects whose Day 29 survival is unknown will be censored at the date of last contact. Source: Listing 16.x.x.x		

Clear Creek Bio., Inc.: Protocol CCB-CRISIS-01
Figure 14.2.3.2

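### The Kaplan-Meier analysis of time to discharge gives in-hospital death no handling of its own; on the natural reading deaths are censored, which overstates cumulative discharge

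*SAP*

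**What the plan says.** Duration of hospitalization is a secondary objective (SAP 1.3.2). Section 2.5.2 says that Kaplan-Meier "estimates and plots will be provided to assess the duration of hospitalization (Study Day at time of initial discharge"). It then gives two censoring rules:

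- Rule 1: "Subjects who were not discharged by the Day 15 visit will be censored at the Day 15 visit".
- Rule 2: "Subjects who did not complete the trial while still hospitalized will be censored at the date of last contact".

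The shell of Table 14.2.2.1 repeats both rules in its footnote and has one row for each under the number censored. The row for rule 2 is labelled "Did Not Complete Study". The shell reports the number discharged, the censored counts and the three quartiles, and it has no row for death. Figure 14.2.2.2 plots the same curve.

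Table 14.1.2 defines completion as "Completed the study (through Day 15"). Section 2.5.2 foresees deaths in this window, because its status summary for Days 3, 5, 7 and 15 begins "Hospitalization status (died, hospitalized in ICU, hospitalized not in ICU, discharged for initial hospitalization and re-hospitalization"). It also plans a separate analysis: "Mortality will be summarized through Day 29 by treatment group".

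**The concern.** Kaplan-Meier assumes that a subject censored on a given day has the same later chance of the event as those still under observation. That is reasonable for someone who is lost to follow-up alive. A subject who has died can no longer be discharged, so death competes with discharge. If the subject is censored at death, the later chance of discharge is spread over the survivors, and the curve rises above the proportion who actually left hospital alive.

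Two things are at stake. First, the curve and quartiles for a named secondary objective can be too favourable, more so in the arm with more deaths. Second, the text does not settle which rule covers a death, so two programmers could follow the SAP and produce different curves.

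**Working it through.** **Which rule covers a death.** Completion means through Day 15, so a subject who dies in hospital on Day 6 has not completed the trial and was still hospitalized. That is rule 2. The same subject was also not discharged by Day 15, which is the wording of rule 1, but a dead subject has no Day 15 visit at which to be censored. Rule 2 is therefore the natural reading. The date of last contact is then at or near death.

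**Inputs.** The SAP states no event rate or estimate for this endpoint, so there is no figure to reproduce. Arm sizes come from SAP 1.2.1 ("approximately 8 subjects assigned to SOC alone and approximately 16 subjects on SOC plus brequinar"). All discharge and death days below are assumed.

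**Formulas.**
- Planned curve: 1 − ∏(1 − dᵢ/nᵢ) over discharge days, where dᵢ is the number discharged, nᵢ the number at risk, and deaths leave the risk set on the day of death (after any discharge on that day).
- Comparator: the same product with deaths kept at risk as undischarged to Day 15. With no other dropout this is the Aalen-Johansen cumulative incidence, and at Day 15 it equals discharges divided by n.
- A quartile is the first day on which the curve reaches 25%, 50% or 75%.

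**One case in full: n = 16 with 4 deaths.** Discharges on Days 3, 4, 5, 6, 7, 8, 8, 9, 10, 11, 12; deaths on Days 4, 5, 7, 8; one inpatient at Day 15.
- Planned: 1 − (15/16)(14/15)(12/13)(10/11)(9/10)(6/8)(4/5)(3/4)(2/3)(1/2) = 90.1%. The curve is at 70.3% on Day 10 and 80.2% on Day 11, so Q3 = Day 11.
- Comparator: 11/16 = 68.75%. The curve never reaches 75%, so Q3 is not reached. The median is Day 9 against Day 8 under the planned rule.

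**Other death counts, n = 16.** One inpatient at Day 15, remaining discharges spread evenly over Days 3 to 12, deaths within Days 4 to 8:

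| Deaths | Planned, Day 15 | Actual, Day 15 | Planned Q1/median/Q3 | Actual Q1/median/Q3 |
|---|---|---|---|---|
| 0 | 93.75% | 15/16 = 93.75% | 5/8/10 | 5/8/10 |
| 1 | 93.1% | 14/16 = 87.5% | 5/8/11 | 5/8/11 |
| 2 | 92.1% | 13/16 = 81.25% | 5/8/10 | 5/8/11 |
| 3 | 91.3% | 12/16 = 75.0% | 5/9/11 | 5/9/12 |
| 4 | 90.1% | 11/16 = 68.75% | 6/8/11 | 6/9/not reached |

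**n = 8 with 2 deaths.** Discharges on Days 3, 5, 8, 10, 12; deaths on Days 4 and 8; one inpatient. Planned: 1 − (7/8)(5/6)(4/5)(2/3)(1/2) = 80.6%, with Q3 on Day 12. Actual: 5/8 = 62.5%, with Q3 not reached.

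**Effect of timing.** In another assumed set with n = 16, 9 discharged, 4 dead and 3 inpatients, the actual figure is 9/16 = 56.2% whenever the deaths occur. The planned curve gives 75.0% if all four die on Day 2, 68.3% if they die on Days 4, 6, 8 and 10, and 56.2% if all die after the last discharge.

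**Constant hazards.** With discharge hazard λ = 0.12 per day and death hazard μ, the planned curve estimates 1 − exp(−15λ) = 83.5% by Day 15, with median ln 2/λ = 5.78 days, for every μ. The cumulative incidence is λ/(λ+μ) × [1 − exp(−15(λ+μ))]. For μ = 0, 0.01, 0.02 and 0.04 it is 83.5%, 79.2%, 75.2% and 68.2%, with medians 5.78, 6.00, 6.25 and 6.87 days. The planned curve does not respond to the death rate at all.

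**The case against.** The strongest reply is that the SAP nowhere says deaths are censored at death. Last contact and date of death are separate fields (Listings 16.2.1 and 16.2.6.5), death is not among the discontinuation reasons in Table 14.1.2, and rule 1 could literally cover a death. Holding deaths to Day 15 would remove the bias. This stands as a limit on certainty, and it also shows that the text must say which rule applies.

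A reader might also infer that a harmful arm would appear to shorten stay. The documents do not support that. In the table above the planned figure falls slightly as deaths rise, from 93.75% to 90.1%, so harm is understated rather than reversed. A shorter median than a death-free arm (8 against 9 days) did arise in one constructed comparison, but only with 4 of 16 subjects dying on Day 2 and an invented comparator with 12 of 16 discharged.

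It is also fair that Table 14.2.2.1 reports quartiles and not a Day 15 percentage, that one death leaves the quartiles unchanged here, and that the number discharged is printed beside N. Deaths can be seen in Table 14.2.1 and in the time-to-death analysis. A careful reader could notice the discrepancy, but none of these outputs corrects the quartiles or the plotted curve.

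Finally, this is a phase 1a trial of about 24 subjects with safety as its primary objective, no primary efficacy analysis, no formal sample size and no planned test of this endpoint. That bears on priority and not on whether the rule is right.

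**Conclusion.** The point holds in limited form. Handling of in-hospital death is not stated, and the natural reading censors it, which overstates cumulative discharge whenever a death precedes a later discharge. In the assumed sets with n = 16 and deaths on Days 4 to 8, the overstatement at Day 15 runs from about 6 percentage points (1 death) to about 21 (4 deaths). With n = 8 and 2 deaths it is about 18. Upper quartiles can be too short, and with 4 of 16 or 2 of 8 deaths a third quartile is reported that is never reached. The bias is zero with no deaths or with all deaths after the last discharge.

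These sizes rest wholly on assumed numbers and timing of deaths, because the SAP gives none. Since the output is descriptive and secondary, this should be fixed before analysis, but it does not threaten the trial's primary conclusions.

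**What to change.** In Section 2.5.2, Table 14.2.2.1 and Figure 14.2.2.2:

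1. State that death before initial discharge is a competing event, and report the Aalen-Johansen cumulative incidence of discharge by arm, with quartiles read from that curve. A simpler alternative is to keep subjects who die at risk as undischarged through Day 15. The two are the same only if there is no other dropout before Day 15, which rule 2 itself anticipates.
2. Reserve censoring at last contact for subjects who are alive at withdrawal or loss to follow-up.
3. Add a 'Died in hospital' row to Table 14.2.2.1, and show a quartile as not reached where the curve does not get there.

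The cost is a few sentences of SAP text, one shell row and its footnote, and a few lines of code. No new data are needed, because the hospitalization log (Listing 16.2.6.4) and date of death (Listing 16.2.6.5) are already planned.

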2.5.3 Exploratory Efficacy Analyses

Changes from baseline will be summarized by treatment:

- Viral load (nasopharyngeal) (Days 3, 5, 7, and 15)
- Inflammatory markers (Days 3, 5, 7, and 15)
- DHO levels (Days 3, 5, 7, and 15)
- Brequinar concentration levels (Days 3, 5 and 7)

For inflammatory markers (including pro-inflammatory cytokines), results from both local and central laboratories will be combined, where the local test result will be normalized where necessary. (See [Section 3.2](#) for normalization method).

Viral culture results will be provided in data listings only.

Confidential Document

	CCB-CRISIS-01 Statistical Analysis Plan	Revision No. 1.0
	Document Date: 17-Dec-2020	Page 10 of 17

2.6 Safety Analyses

Adverse Events

An overall summary of treatment-emergent adverse events (TEAEs) will be presented by treatment and total, including the total number of events, frequency counts and percentages for:

- Any TEAE
- Treatment-related TEAEs
- CTCAE Grade 3 or above TEAEs
- TEAEs leading to drug withdrawn
- TEAEs leading to study discontinuation
- Serious TEAEs
- Fatal TEAEs
- TEAEs of interest

The incidence of TEAEs by treatment and total will be tabulated by MedDRA system organ class and preferred term for:

- All TEAEs
- Treatment-related TEAEs
- TEAEs by severity
- TEAEs leading to study discontinuation
- Serious TEAEs
- TEAEs of interest

AEs will be considered treatment-emergent if the onset date is on or after the day of randomization. “Drug related” will include ‘Definite’, ‘Probable’ and ‘Possible’ relationship to drug as determined by the Investigator.

Safety Laboratory Assessments

Safety laboratory tests (Chemistry and Hematology) will be performed throughout the study. Laboratory parameters of interest (AST, ALT, ALP, Total Bilirubin, Creatinine, Hemoglobin, WBC, Absolute Neutrophils, Absolute Lymphocytes and Platelets) will be summarized for changes from baseline.

Confidential Document

	CCB-CRISIS-01 Statistical Analysis Plan	Revision No. 1.0
	Document Date: 17-Dec-2020	Page 11 of 17

NCI CTCAE grades will be derived for the lab parameters included in [Appendix 1](#) and presented in data listings. Separate listings of Grade 3 or 4 values will also be provided.

